### **8.5.1.3 Statistical Significance**

Unless otherwise specified, statistical testing will be performed at the two-sided 0.05 significance level unadjusted for multiple testing. P-values will be rounded to three decimal places. If a p-value is less than 0.001, it will be reported as "<0.001". If a p-value is greater than 0.999, it will be reported as ">0.999".

### **8.5.1.4 Reporting Precision**

Unless otherwise specified, the following conventions will apply for data displayed. In general, percentages will be displayed to 1 decimal place. Percentages <0.05% will be reported to 2 decimal places. For continuous parameters, means and medians will be reported to 1 additional decimal place than the measured value. In contrast, the standard deviation will be reported to 2 additional decimal places than the measured value. Minimum and maximum values will be reported to the same precision as the measured value.

### **8.5.1.5 Missing Data**

All attempts will be made to limit the amount of missing data. For all analyses of the primary endpoints, the number of observations available will be reported so the reader can assess the impact of missing data. For all clinical endpoints except for the patient-reported outcome measurements, an adjustment to the denominator will be made based on the amount of evaluable data. For each visit (or reporting time point), the event rate will be calculated as the number of subjects with certain event terms over the number of evaluable subjects. The evaluable subjects at each reporting time point include all subjects who are enrolled and

- 1) had an event within (on or before) the reporting cutoff days, or

- 2) had a follow-up at or after the lower limit of the reporting window, or
- 3) the withdrawal consent date/recorded lost-to-follow-up date at or after the lower limit of the reporting window.

### 8.5.1.6 Adverse Event Dates

More generally, in the case of partial adverse event onset date or date of death, the unknown portion of the date of the event will be imputed. If the month and year are known, the 15th of the month will be used for analysis. If only the year is known, the event will be analyzed as if it occurred on June 30th of the known year. In the rare case that the date is fully unknown, the date will be imputed as the initial treatment date. Imputation of partial dates is subject to the condition that it must occur on or after the initial treatment date. In the case where the imputed date is before the initial treatment date, the date of the initial treatment will be used. As death cannot occur before any documented subject contact, for date of death, the imputed date of death must occur on or after the last known contact in the study.

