#### **8.1.2 Secondary Endpoints**

The following are the secondary endpoints:

- IPSS measured at 3, 12, and 24 months post-baseline
- Device or Procedure-Related Adverse event rate at post-procedure, 3, 12, and 24 months
- Technical Success defined as the successful embolization of the treated prostate gland
- Frequency of indwelling bladder catheter removal post PAE at 3, 12, and 24 months
- Number of patients and types of treatment for refractory or recurrent LUTS due to BPH post PAE at 3, 12, and 24 months
- Change from baseline in Sexual Health Inventory for Men (SHIM) at 12 months post-PAE.

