### 8.5.4 Safety Analyses

All device or procedure related adverse events (AEs) collected will be summarized cumulatively throughout the follow-up time. The frequency count of AEs and the unique number of subjects who had the AEs will be presented. Also, the frequency and percentage of patients who had a Serious AE (SAE), or a treatment-related serious AE will be tabulated separately. If a patient experienced multiple AEs, only the most severe event or the most intense relationship to the study device would be counted within an AE code. The following information will be reported about each AE; start date, stop date, severity, relationship, expectedness, outcome, and duration.

The time-sensitive nature of any response variable may be displayed by using a Kaplan-Meier plot.

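### Partial adverse event onset dates are imputed with a lower limit but no upper limit, so an onset can fall after the event's own stop date or the contact that first reported it

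*Combined protocol and SAP*

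**What the plan says.** Section 8.5.1.6 gives three rules for an incomplete onset date.

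- Month and year known: "If the month and year are known, the 15th of the month will be used for analysis".
- Year known: "If only the year is known, the event will be analyzed as if it occurred on June 30th of the known year".
- Nothing known: "In the rare case that the date is fully unknown, the date will be imputed as the initial treatment date".

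One constraint follows: "Imputation of partial dates is subject to the condition that it must occur on or after the initial treatment date". The section has one further bound. It applies to deaths and is also a lower one: "the imputed date of death must occur on or after the last known contact in the study". No section limits an imputed onset from above.

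The imputed date is used in several places. Section 8.1.2 lists as a secondary endpoint the "Device or Procedure-Related Adverse event rate at post-procedure, 3, 12, and 24 months". Section 8.5.1.5 makes a subject evaluable at a time point if, among other routes, he "had an event within (on or before) the reporting cutoff days, or"; the number of cutoff days is not given. Section 8.5.4 adds: "The following information will be reported about each AE; start date, stop date, severity, relationship, expectedness, outcome, and duration". Section 8.5.3.2 sends the reader to section 9.3 for the event rates, but 9.3 holds only the definition of a serious event, so nothing there overrides the date rule.

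**The concern.** An onset later than the event's own resolution, or later than the visit at which the site heard of it, is impossible on data already in the case report form. Section 8.5.1.6 applies this kind of check to deaths, tying the imputed date to documented contact, but has no matching check for onsets.

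Three outputs depend on the date.

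- **Durations and listings.** An onset after the stop date makes the duration meaningless. Section 8.5.1.2 defines duration as start minus end, so the impossible case comes out positive and a check for negative values would miss it.
- **Rates by time point.** If events are assigned by date, an onset moved past a cutoff leaves the numerator. The subject usually stays in the denominator through his follow-up visit, so the rate falls.
- **Time in study.** Section 8.5.1.2 counts event onset among the dates that set last contact, so an onset imputed after study exit would lengthen apparent follow-up.

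**Working it through.** The plan states no figure on this point, so there is none to reproduce. The check applies the rule as written.

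**Rule (section 8.5.1.6)**
- Month known: imputed onset = max(15th of the onset month, procedure date).
- Year only: imputed onset = max(30 June of the onset year, procedure date).

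**Assumptions, because the documents give no figures**
- The 3-month cutoff is day 90, or day 90 + 14 = 104 using the visit window in Table 1.
- Each of 365 procedure dates and each true onset day is equally likely.
- Events last 3, 7, 14 or 28 days.

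**Largest forward shift**
- Month known: 15 − 1 = 14 days.
- Year only: 1 January to 30 June = 180 days.

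**Two examples**
- Year only. Procedure 10 January, true onset 12 January, stop 17 January, 4-week visit 7 February. The imputed onset is 30 June, day 171. That is 164 days after the stop date, after the visit, and outside 3 months.
- Month known. Procedure 8 February, true onset 1 March, stop 5 March, visit 8 March. The imputed onset is 15 March, day 35. That is 10 days after the stop date and after the visit, but still inside 3 months.

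**All combinations.** These number 365 × 29 = 10,585 for onsets on days 0–28, 365 × 91 = 33,215 for days 0–90, and 365 × 105 = 38,325 for days 0–104. Paired values are for cutoff day 90 / day 104.

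| Share of partially dated events | Month known | Year only |
|---|---|---|
| Imputed after stop, 3-day event | 36.2% | 48.5% |
| Imputed after stop, 7-day event | 23.0% | 47.4% |
| Imputed after stop, 14-day event | 0% | 45.5% |
| Imputed after stop, 28-day event | 0% | 41.6% |
| True onset day 0–28, dated past the cutoff | 0% / 0% | 28.5% / 24.7% |
| True onset day 0 to cutoff, dated past it | 3.8% / 3.3% | 37.0% / 35.1% |
| True onset after cutoff to day 365, dated inside it | 1.5% / 1.6% | 17.0% / 17.9% |
| True onset day 0–28, dated later than the truth | 46.0% | 49.3% |
| True onset day 0–28, dated earlier than the truth | 48.9% | 48.7% |

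For the 12-month rate, 17.2% of year-only events with true onset on days 106–365 are dated past day 365. With the cutoff at 365 + 56 = 421 and onsets on days 106–421, the share is 14.1%.

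**With an upper limit.** The imputed onset was capped at the earlier of the stop date and the next nominal visit (day 28, 91 or 365), for events of 7 to 14 days.
- Year-only events lost from the 3-month rate fall from 37.0% to 3.7–7.3% (day 90) and from 35.1% to 3.2–5.9% (day 104).
- Month-known losses change little: from 3.8% to 2.8–3.8% and from 3.3% to 2.4–3.3%.
- At a day-91 cutoff both fall to 0%, because the nominal visit then coincides with the cutoff.

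The cap cannot make a date worse. The stop date and the first report are never before the true onset, so a capped date lies between the true onset and the uncapped imputation.

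**Scale on the rate.** Assume 450 evaluable subjects (500 less 10%, borrowing the missing-IPSS allowance in section 8.3). Each subject moved across a cutoff changes that rate by 1/450 = 0.22 percentage points.

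**The case against.** The strongest case against is that few events will be affected. Before 3 months, events are collected at the procedure, at 4 weeks and at 3 months, and patients receive a form for recording events in the first month (section 6.2). A site that hears of an event at such a contact but knows only its year should be rare. The 9- and 12-month gaps between contacts come only after the 3-month visit. This stands, and it keeps the point minor.

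It can also be said that assignment by date is not certain. Section 8.5.1.2 analyses visit assessments by the visit entered in the eCRF, and the cumulative counts in section 8.5.4 do not depend on onset. The primary endpoint is untouched. This limits the effect on the rates, but the reported start dates and durations would still be wrong.

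Two stronger readings are tempting, and the documents support neither.

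- A reader might infer that the rule systematically hides early complications. It does not work in one direction. Imputed dates that precede the procedure are reset to day 0, fully unknown dates also go to day 0, earlier and later shifts are about equally frequent, and 17.0–17.9% of later year-only events move into the 3-month rate.
- A reader might infer that the 15th-of-month rule removes early events from the 3-month rate. With a shift of at most 14 days, no onset on days 0–28 leaves it. Only onsets in the last 14 days before the cutoff can. Large moves come from the 30 June rule alone.

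**Conclusion.** The point holds as a minor defect in a stated rule. Section 8.5.1.6 allows onset dates that the trial's own data show to be impossible. The month-known rule mainly damages durations and the order of dates. The year-only rule can also misplace an event between the 3-month and 12-month rates: 35% to 37% of year-only events truly within 3 months are dated past the assumed cutoff.

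These percentages rest on uniform procedure and onset dates and on assumed cutoffs and event lengths. They are shares of partially dated events, not of all events. The number of partial dates is not given and is probably small before 3 months. The net bias in the rates cannot be signed from the documents.

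**What to change.** Keep the 15th and 30 June imputations and add one sentence to section 8.5.1.6: an imputed onset may not be later than the earliest of the event's known stop date, the date of the visit or report that first recorded it, and death, and may not be earlier than the initial treatment date. Where the stop date is itself partial, the report date still gives a limit.

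Do not replace the mid-period dates with the earliest date consistent with the known part. The missing cap does not require it. It would move 62% to 64% of year-only events with true onset after the cutoff (up to day 365) into the 3-month rate, against 17% to 18% under the present rule (cutoff day 90 to 104).

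The cost is one derivation step, and the rates at the time points may change slightly. The cap only moves dates earlier, so it leaves uncorrected those events that the present rule dates too early.

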### 8.5.1.7 Analytical Methods

Time-dependent response variables will be expressed using the Kaplan-Meier curve, and the hazard ratio and the 95% confidence limit will be reported. Data for all categorical endpoints (e.g., TLF rate at a specific time point, etc.) are shown with the number of patients, percentage, and Clopper-Pearson's exact 95% confidence interval. Differences between treatment groups are shown using a 95% confidence interval of the difference. Analyses of secondary endpoints are conducted with the FAS population.

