## 4 Study Design

This is a prospective, open label post market study to evaluate the long-term safety and effectiveness of PAE using Embosphere Microspheres. Up to 500 patients with LUTS due to BPH will be enrolled in this single arm post market study. All patients at sites who meet eligibility criteria will be offered participation. Long term effectiveness of PAE on LUTS will be evaluated by IPSS score at baseline, 3 months, 12 months, and 24 months. Note: All subjects will be asked to complete the IPSS. However, study subjects who have an indwelling bladder catheter will not be required to complete the IPSS; the IPSS questions may not be relevant to subjects with an indwelling bladder catheter. Safety will be assessed by evaluating device and procedure-related adverse events at the same time points, plus at 4 weeks following embolization. Erectile function will be assessed at baseline and 12 months by SHIM score. Additional treatments for refractory or recurrent LUTS due to BPH post prostatic artery embolization will also be recorded.

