### **8.5.3.5 Number of patients and types of treatment for refractory or recurrent LUTS due to BPH post-PAE**

The types of treatment and the number of patients that received that treatment for refractory or recurrent LUTS due to BPH post-PAE will be reported at 3, 12, and 24 months, and overall will be reported using the FAS.

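### Section 8.5.1.7 promises a hazard ratio that a single-arm cohort cannot supply and states no Kaplan-Meier estimate in its place; the fixed-time rates that remain tend to run high when men drop out

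*Combined protocol and SAP*

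**What the plan says.** Section 4 describes the design: up to 500 men "will be enrolled in this single arm post market study". There is no control group.

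Section 8.5.1.7 (Analytical Methods) makes three statements that matter here:

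- Time-to-event display: variables of this kind get a Kaplan-Meier curve, and "the hazard ratio and the 95% confidence limit will be reported". No reference group or model is named.
- Categorical endpoints, with a TLF rate as the example, "are shown with the number of patients, percentage, and Clopper-Pearson's exact 95% confidence interval".
- In a separate sentence after that one: "Differences between treatment groups are shown using a 95% confidence interval of the difference".

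Section 8.5.1.5 (Missing Data) sets the rate at each reporting time for clinical endpoints other than patient-reported outcomes: "the event rate will be calculated as the number of subjects with certain event terms over the number of evaluable subjects". A man is evaluable if he had the event by the cutoff, was followed to at least the lower limit of the window, or withdrew or was recorded as lost at or after that limit.

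For additional treatment of refractory or recurrent symptoms, Section 8.5.3.5 reports "The types of treatment and the number of patients that received that treatment" at 3, 12 and 24 months and overall. Section 8.5.4 makes a Kaplan-Meier plot optional and mentions no hazard ratio. Section 7 discontinues a man, and stops his data collection, after any non-PAE BPH procedure other than biopsy.

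**The concern.** A hazard ratio compares two hazards. With one arm and no named comparator, an output that the SAP makes mandatory is undefined for the cohort. The analyst must either drop it or choose a comparison later, possibly with the data in view. The wording on treatment groups and TLF, like the reference to randomization in Section 8.5.1.2, does not fit this design.

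The second part is what is absent. Where a Kaplan-Meier curve is used, the SAP gives no event-free probability with a confidence interval at a set time, no named event and no censoring rule. Section 2 gives long-term safety and effectiveness as the goal, and Section 3.2 lists additional treatment after PAE as a secondary objective. At 24 months, how early exits are handled affects the reported retreatment and adverse event rates. The fixed-time rate that remains handles them in a way that pushes the rate upward.

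**Working it through.** The documents give no event rate, event count, hazard ratio or survival estimate, so there is no planning figure to reproduce. All event and dropout rates below are assumptions.

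**1. Is the hazard ratio defined?** Section 4 gives one arm. Section 8.5.1.7 gives no reference group and does not restrict the hazard ratio to subgroups. For the whole cohort it is undefined. Between two-level subgroups in Section 8.5.7 (for example bilateral against unilateral) it could be computed. With d events and share q of men in one subgroup, the 95% CI is the estimate divided and multiplied by exp(1.96/√(d·q·(1−q))). Assume 500 men and 10% with an event, so d = 50:

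- 50:50 split: exp(1.96/√12.5) = 1.74
- 80:20 split: exp(1.96/√8) = 2.00
- 90:10 split: exp(1.96/√4.5) = 2.52

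**2. What can one arm give?** A Kaplan-Meier event probability with its CI needs no comparator. With 500 men, an assumed 10% risk and no censoring, the half-width is 1.96·√(0.10·0.90/500) = 0.026, or 2.6 points. The exact binomial interval already planned is also valid: 45/450 = 10.0%, 95% CI 7.4% to 13.2%. (Here 450 is 500 less 10%, borrowing the missing share that Section 8.3 plans for IPSS.) Without dropout, then, little separates the two.

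**3. What does the Section 8.5.1.5 denominator do with dropout?** It keeps every man with an early event and removes event-free men who left before the window. Assume constant, independent event and dropout hazards over 24 months and, at first, ignore the window width. Write a = −ln(1 − true risk) and c = −ln(1 − dropout).

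- Probability that an event is observed: E = a/(a+c) · [1 − (1 − risk)(1 − dropout)]
- Probability of being event-free and still followed: S = (1 − risk)(1 − dropout)
- Planned rate: E/(E + S)

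| Assumed true risk | Assumed dropout | a | c | E | S | E/(E+S) |
|---|---|---|---|---|---|---|
| 10% | 20% | 0.1054 | 0.2231 | 0.0898 | 0.72 | 11.1% |
| 20% | 30% | 0.2231 | 0.3567 | 0.1693 | 0.56 | 23.2% |

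Under these assumptions Kaplan-Meier targets 10% and 20%. A raw count over all men treated would give E itself, 9.0% and 16.9%, which is too low.

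**4. Does the visit window change this?** The 24-month window opens 56 days early. Taking 24 months as 730 days, event-free men who leave after day 674 stay in the denominator. They add W = c/(a+c) · [e^(−(a+c)·674/730) − e^(−(a+c))], which is 0.0125 and 0.0157. The planned rates become 0.0898/0.8223 = 10.9% and 0.1693/0.7450 = 22.7%. The upward shift is smaller but remains.

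**5. How does Section 7 interact?** A non-PAE BPH procedure ends follow-up. For additional treatment, that procedure is the event. For adverse events, it is an early exit. Treating it as censoring in a retreatment analysis would remove the very events being counted, and the SAP states no rule.

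**The case against.** A reader might infer that time-dependent outcomes are left with no usable estimate. The documents do not support that. The Kaplan-Meier curve is itself a one-sample estimate. Sections 8.5.1.5 and 8.5.1.7, read with Section 8.5.3.5, can be taken to give the proportion retreated by each time with an exact CI, although Section 8.5.3.5 alone names only types and numbers. Section 8.1.2 defines no endpoint as time-to-event: adverse events, catheter removal and additional treatment are rates or counts at fixed times.

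Three other strong readings also fail:

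- **Treatment-group differences as the time-to-event summary.** That sentence follows the one on categorical endpoints and is not tied to time-dependent variables.
- **A hazard ratio as impossible anywhere in this study.** Section 8.5.7 plans two-level subgroup comparisons on the secondary endpoints, where one could be formed.
- **Freedom from retreatment as the central outcome.** The primary objective and endpoint concern IPSS, and additional treatment is secondary.

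It can fairly be added that a time-to-first-treatment analysis goes beyond the listed endpoint. That stands, but the analysis summarises a listed endpoint with early exits handled properly. The objection does not remove the mandatory output with no comparator, the absence of any stated Kaplan-Meier estimate, or the upward pull in the rates.

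**Conclusion.** The point holds as a minor one. The hazard ratio in Section 8.5.1.7 is undefined for the cohort as written, the treatment-group and TLF wording does not fit the trial, and no numerical Kaplan-Meier summary is specified. The 12-month IPSS analysis in Section 8.5.2 is untouched.

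The numerical consequence lies in the fallback rates. It is about 1 point at an assumed 10% risk with 20% dropout, and about 3 points at 20% with 30% dropout. The no-censoring 95% half-widths with 500 men are 2.6 and 3.5 points respectively. These sizes rest on constant hazards and on dropout independent of the event. With no dropout the shift vanishes; with informative dropout the simple Kaplan-Meier estimate would be biased too.

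**What to change.** Revise the SAP before analysis:

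1. In Section 8.5.1.7, replace the hazard ratio with the Kaplan-Meier estimate, or cumulative incidence with death as a competing event, and its 95% CI at 3, 12 and 24 months.
2. Apply this at least to first additional BPH treatment after PAE (Sections 8.1.2 and 8.5.3.5). Take the first PAE as time origin, and count a procedure that triggers discontinuation under Section 7 as an event, not as censoring. State whether medication counts as treatment, and how a repeat PAE is distinguished from a further PAE that completes the initial treatment, since Section 7 treats these as separate cases.
3. Confine any hazard ratio or between-group difference to the Section 8.5.7 subgroups, naming the two groups compared.
4. Delete the TLF and treatment-group wording.
5. Make Section 8.5.1.7, where Kaplan-Meier is mandatory, agree with Section 8.5.4, where it is optional.

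The cost is SAP wording and some programming. No new data are needed, provided that the case report form records the date of each additional treatment; the documents list additional procedures and medications as collected but do not list that field.

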## 8.5.2 Analysis of the Primary Endpoint

The stratified sample mean change from baseline in 12 month IPSS is estimated as follows.

$$\bar{x} = \sum_{h=1}^L \frac{N_h}{N} \sum_{i=1}^{n_h} \frac{X_{hi}}{n_h} = \sum_{h=1}^L \frac{N_h}{N} \bar{x}_h$$

where  $\bar{x}$  is the stratified sample mean,  $L$  is the number of strata,  $X_{hi}$  is change from baseline in 12 month IPSS for the  $i^{th}$  patient in the  $h^{th}$  stratum,  $N$  is the overall sample size and  $N_h$  is the sample size in stratum  $h$

It can be shown in T. Yahane(1967) that the expected value and variance of  $\bar{x}$  ( $V(\bar{x})$ ) assuming sampling without replacement are

$$E(\bar{x}) = \mu$$

$$V(\bar{x}) = \sum_{h=1}^L \left(\frac{N_h}{N}\right)^2 \left(\frac{N_h - n_h}{N_h n_h}\right) S_h^2$$

$$S_h^2 = \frac{1}{N_h - 1} \sum_{i=1}^{N_h} (X_{hi} - \mu_h)^2$$

where

The 95% confidence interval ( $CI(\mu)$ )s calculated as follows:

$$CI(\mu) = \bar{x} \pm z_{1-\alpha/2} \sqrt{\hat{V}(\bar{x})}$$

where  $\alpha$  is the type I error and  $\hat{V}(\bar{x})$  is the unbiased estimator of  $V(\bar{x})$  and is calculated as follows:

$$\hat{V}(\bar{x}) = \sum_{h=1}^L \left(\frac{N_h}{N}\right)^2 \left(\frac{N_h - n_h}{N_h n_h}\right) S_h^2$$

$$s_h^2 = \frac{1}{n_h - 1} \sum_{i=1}^{n_h} (X_{hi} - \bar{x}_h)^2$$

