## 8.2 Primary Statistical Objective

The primary statistical objective is to evaluate the efficacy of the device by estimating the change from baseline in the 12 month IPSS within +/- 1 unit.

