## 8.3 Sample Size

The sample size is based on the following assumptions

- Four countries with asymmetrical countrywide enrollments ranging from 15% to 25% of the total enrollment (conservative assumption)
- Standard Deviation = 8.5
- Difference between the lower and upper 2-sided 95% Confidence interval = 2
- 10% of patients missing either baseline or 12 month IPSS

A sample size of up to 500 patients is required to estimate the 12 month change from baseline in the IPSS within +/- 1 unit. Sample size calculations were performed using NCSS PASS 2020's procedure for one mean in a stratified design.

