## 8.5.3 Analysis of the Secondary Endpoints

### 8.5.3.1 IPSS changes over time

The changes over time in the IPSS using the EAS will be modeled using a linear mixed model where country and patient will be considered a random effect. If there is evidence of non-linearity, a nonlinear mixed-effects model using a 3rd-degree

 Tibshirani, Robert (1996). "Regression Shrinkage and Selection via the lasso". Journal of the Royal Statistical Society. Series B (methodological). Wiley. 58 (1): 267–88. JSTOR 2346178.

polynomial will be implemented. The predicted curve and 95% confidence interval will be reported. Missing data will not be imputed.

Sensitivity analyses using complete cases and missing values replaced with an age-specific average will be performed.

A multivariate linear model will be developed to predict the IPSS changes over time. Univariate analysis will be performed analyses for all the baseline characteristics. Based on those results combined with clinical judgment, a final set of baseline characteristics will be created for use in the multivariate model. The LASSO regression analysis method will be used to perform variable selection and regularization.

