### 8.5.7 Subgroup Analyses

The following subgroups will be evaluated for the primary and secondary endpoints:

- Patients treated with Embosphere Microspheres 100-300 $\mu$  vs. 300-500 $\mu$
- Comparison of procedure time for patients embolized with radial vs. femoral access
- Embolizations that were/were not performed using the PErFecTED technique
- Bilateral vs. unilateral embolizations

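### The primary 12-month IPSS interval and the secondary mixed model have no site term, so the 95% CI is too narrow for real-world inference if outcomes vary by site

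*Combined protocol and SAP*

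**What the plan says.** - **Recruitment.** Section 4 brings men in through sites: "All patients at sites who meet eligibility criteria will be offered participation". Section 17 provides for monitoring of each centre. The number of sites is not given.
- **Aim.** Section 2 sets out to evaluate long-term safety and effectiveness in real-world use. Section 8.2 makes this "estimating the change from baseline in the 12 month IPSS within +/- 1 unit".
- **Sample size (8.3).** The inputs are "Standard Deviation = 8.5", "Difference between the lower and upper 2-sided 95% Confidence interval = 2" and "10% of patients missing either baseline or 12 month IPSS", with four countries as strata and a ceiling of 500 patients. The procedure is for one mean in a stratified design. No ICC, cluster size or design effect is listed.
- **Primary analysis (8.5.2).** "The stratified sample mean change from baseline in 12 month IPSS is estimated as follows": country means are weighted by N_h/N. The variance is a sum of squared weights times the patient-level s_h² and a factor in N_h and n_h.
- **Secondary model (8.5.3.1).** IPSS over time is "modeled using a linear mixed model where country and patient will be considered a random effect". Site does not appear.
- **Subgroups (8.5.7).** The comparisons include "Embolizations that were/were not performed using the PErFecTED technique", particle size and bilateral against unilateral treatment. No test or model is named.

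**The concern.** The plan allows for grouping by country but leaves out the level at which men are selected and treated. Section 6.2 records access route, PErFecTED use, particle size and volume at each procedure, and these may follow the habits of an operator or centre. Section 5 lets the investigator exclude a man for any other reason, so selection can also differ by site.

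The primary result is a single-arm absolute mean, so site effects cannot cancel between arms as they may in a randomised comparison. If men at one site resemble each other more than men at different sites in the same country, patient-level variance divided by n_h understates the error of the mean. The published interval would then cover the real-world mean less often than 95%, and the precision claim would rest on the wrong standard error.

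**Working it through.** **Inputs.** SD 8.5, 95% two-sided interval, half-width 1, 10% missing and up to 500 patients all come from section 8.3. The plan does not say that 8.5 is the SD of the change score; I take it as such. ICC and number of sites are assumptions.

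**1. The plan's own figure.** n = (1.96 × 8.5 / 1)² = 277.6, so 278 evaluable men; 278 / 0.90 gives 309 enrolled. The printed inputs therefore do not lead to 500. With 500 enrolled and 450 evaluable, the half-width without clustering is 1.96 × 8.5 / √450 = 0.785.

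**2. Room before plus or minus 1 is missed.** (1 / 0.785)² = 1.62. The target holds up to a design effect of 1.62.

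**3. Effect of site.** I drop the finite-population factor, because as printed it would by itself shrink the half-width to 0.785 × √(50/500) = 0.25. With m = 450 / sites:

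- design effect D = 1 + (m − 1) × ICC
- true half-width = 0.785 × √D
- actual coverage of the nominal 95% interval = 2Φ(1.96/√D) − 1

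| Equal sites | m | ICC | D | Half-width | Coverage |
|---|---|---|---|---|---|
| 20 | 22.5 | 0.01 | 1.22 | 0.87 | 92.5% |
| 20 | 22.5 | 0.05 | 2.08 | 1.13 | 82.6% |
| 20 | 22.5 | 0.10 | 3.15 | 1.39 | 73.1% |
| 30 | 15 | 0.01 | 1.14 | 0.84 | 93.4% |
| 30 | 15 | 0.05 | 1.70 | 1.02 | 86.7% |
| 30 | 15 | 0.10 | 2.40 | 1.22 | 79.4% |
| 50 | 9 | 0.01 | 1.08 | 0.82 | 94.1% |
| 50 | 9 | 0.05 | 1.40 | 0.93 | 90.2% |
| 50 | 9 | 0.10 | 1.80 | 1.05 | 85.6% |

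**4. ICC at which the half-width reaches 1.** 0.62 / (m − 1) gives 0.014 with 10 sites, 0.029 with 20, 0.044 with 30, 0.061 with 40 and 0.078 with 50. These use the normal quantile. A t quantile lowers them: with 20 sites and 4 countries (16 df, quantile 2.12) the limit on D is 450 / (2.12 × 8.5)² = 1.39, so the ICC limit is 0.39 / 21.5 = 0.018.

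**5. Check by simulation** (4,000 trials per setting, four countries, about 450 men). At ICC 0.05 the plan's interval, without the finite-population factor, covered 83%, 86% and 90% with 20, 30 and 50 equal sites, and 78%, 83% and 88% with unequal sites. A site-clustered interval with t on sites minus countries degrees of freedom covered 95% with equal sites. With unequal sites it covered 92%, 93% and 94%. Its half-width averaged about 1.2, 1.1 and 0.95 to 0.98, against a reported 0.78.

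**6. If fewer men are evaluable.** At 278 evaluable there is no room and any positive ICC misses plus or minus 1. Men with a catheter at the end of the procedure are outside the evaluable set (8.4.2). If their share were the 54/286 = 18.9% catheterised at baseline in the cohort in section 1, 500 × 0.811 × 0.90 = 365 would remain, with an unclustered half-width of 0.87 and a limit of (1 / 0.872)² = 1.32.

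**The case against.** **The target may be the participating sites only.** The 8.5.2 variance is design-based, with patients sampled within strata. If inference stops at men treated at these sites, site differences are fixed and already part of s_h². That is a coherent position, but the plan does not state it, and the real-world aim in section 2 points beyond the enrolled centres.

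**The deciding inputs are missing from the documents.** This stands. Over ICC 0.01 to 0.10 the effect runs from trivial to severe, and ICC 0.05 is only an illustration.

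**A reader might infer that the plus or minus 1 precision is necessarily overstated.** The documents do not support that. At 450 evaluable men there is room up to a design effect of 1.62, and 50 sites at ICC 0.05 stay inside the target.

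**A reader might also infer that section 8.5.7 commits to tests with an inflated false-positive rate.** It names no test, and section 3.3 lists the same comparisons as exploratory, so no error rate can be attributed to it. What stands is narrower: an exposure linked to site may be confounded with site.

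**The finite-population factor is the larger defect in the same formula.** True, but removing it still leaves an interval that ignores site.

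**Conclusion.** The omission is a matter of text: the study is multi-site, and neither 8.5.2 nor 8.5.3.1 has a site term. For inference beyond the enrolled centres, any positive within-site correlation with more than one man per site makes the primary interval too narrow.

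The size is conditional on an assumed ICC and number of sites, 450 evaluable men, SD 8.5 and the finite-population factor removed. At ICC 0.05 coverage is about 83%, 87% and 90% with 20, 30 and 50 equal sites, and lower if site sizes vary. At ICC 0.01 with 30 or more sites the loss is 1 to 3 points. Missing the plus or minus 1 target requires a design effect above 1.62, for example an ICC above about 0.03 with 20 sites. That room is not assured, because 500 is a ceiling and the plan does not say what the excess over 309 is for. The change is cheap and should be made.

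**What to change.** - **8.5.2.** State the population to which the mean is meant to apply, and the number of sites. Keep the country-stratified mean. Compute its variance with site as the sampling unit within country: V = Σ_h [N_h / (N n_h)]² × k_h/(k_h − 1) × Σ_j (T_hj − T̄_h)². Here T_hj is the sum of residuals from the country mean at site j, T̄_h is the mean of those sums within country h, k_h is the number of sites and n_h is the number of men analysed. Dividing by N² instead would understate the standard error by 10% when N = 500 and 450 are analysed proportionally. Use a t quantile on sites minus countries degrees of freedom.
- **Software.** In SURVEYMEANS use STRATA country, CLUSTER site and WEIGHT N_h/n_h. Without the weight it does not reproduce the N_h/N mean. Let the written formula govern and check the program against it.
- **Before database lock.** Fix a rule for very small sites and for any country with one site, where k_h/(k_h − 1) is undefined; for example, collapse that country with another for variance estimation.
- **8.2 and 8.3.** Report the half-width of this interval against plus or minus 1, and state an assumed ICC.
- **8.5.3.1.** Add a site random intercept.
- **8.5.7.** Include site in any model used, and note that exposures linked to site may be confounded with it.

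**Cost.** SAP wording and a few lines of code, with no extra patients or visits. With no site effect the half-width is about 0.79 to 0.85 instead of 0.78 to 0.79. If sites differ, the interval is wider and less favourable. With about 20 very unequal sites, coverage stays slightly short of nominal, at about 92%.
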